### **8.4.1 Physical Examination**

A complete physical examination will include, at a minimum, assessments of the skin, cardiovascular, respiratory, gastrointestinal and neurological systems. Weight will also be measured and recorded.

Height will be measured at screening only.

### **8.4.2 Skin Evaluation**

Subjects are expected to manifest skin findings associated with psoriasis which may include stable disease, worsening disease, or improving disease.

If a subject develops a clinically significant cutaneous rash that is not typical of a psoriatic picture, then the following evaluations should be conducted:

- Photographs

- o Upper and lower body, front and back, 4 pictures in total. Further close up pictures (15cm x 15cm, 6 inches x 6 inches) should be taken of any areas of interest.
- Skin biopsy
  - o Two  $\geq$ 4mm punch biopsies, one of normal skin, one within the rash.
- Skin culture

Detailed instructions for these evaluations will be provided as Skin Evaluation Instructions for the study.

The Medical Monitor should be notified if photographs/skin biopsy/skin culture are being conducted and the subject should be treated as indicated while he/she continues study therapy.

#### **8.4.3 Vital Signs**

Vital signs will be measured after at least 5 minutes rest, and will include temperature (oral, axillary, core, temporal, or tympanic), sitting or supine blood pressure and heart rate.

#### **8.4.4 Electrocardiograms**

12-lead ECG will be obtained as outlined in the SoA (see Section 1.3) using an ECG machine that automatically calculates the heart rate and measures PR, QRS, QT, and QTc intervals.

At each time point, triplicate ECGs are required. Three individual ECG tracings should be obtained as closely as possible in succession, but no more than 2 minutes apart. The full set of triplicates should be completed in less than 4 minutes.

ECG should also be performed at any time in the study if clinically indicated.

Digital ECGs will be transmitted to a central vendor who will assess ECG measurements for screening requirements prior to randomization.

The investigator is to assess ECG measurements for safety and should report any clinically significant findings as adverse events.

#### 8.4.5 Clinical Safety Laboratory Assessments

See Section 10.2, Appendix 2 for the list of clinical laboratory tests to be performed by the central laboratory and the SoA (Section 1.3) for the timing and frequency.

The investigator must review the laboratory report, document this review, and record any clinically relevant changes occurring during the study in the AE section of the eCRF. Laboratory reports must be filed with the source documents. Clinically significant abnormal laboratory findings are those which are not associated with the underlying disease, unless judged by the investigator to be more severe than expected for the subject's condition.

All laboratory tests with values considered clinically significantly abnormal during participation in the study or within eight weeks after the last dose of study drug should be repeated until the values return to normal or baseline or are no longer considered clinically significant by the investigator or Medical Monitor.

- All protocol-required laboratory assessments, as defined in Section 10.2, Appendix 2, must be conducted in accordance with the laboratory manual and the SoA (Section 1.3).
- If laboratory values from non-protocol specified laboratory assessments performed at the study site's local laboratory require a change in subject management or are considered clinically significant by the investigator (e.g., SAE or AE or dose modification), then the values must be recorded in the eCRF.

#### 8.4.6 Depression and Suicidal Risk Monitoring

In studies of brodalumab, there have been reports of suicidal ideation or behavior. The sponsor considers it important to monitor for such events before and during this clinical study.

Subjects being treated in this study should be monitored appropriately and observed closely for suicidal ideation and behavior or any other unusual changes in behavior. Consideration should be given to discontinuing study drug in subjects who experience signs of suicidal ideation or behavior.

Families and caregivers of study subjects should be instructed to monitor for the emergence of unusual changes in behavior, as well as the emergence of suicidal ideation and behavior, and to report such symptoms immediately to the study investigator.

Baseline assessment of suicidal ideation and behavior and treatment-emergent suicidal ideation and behavior will be assessed during the study using the electronic Columbia Suicide Severity Rating Scale (e-C-SSRS). Depression will be assessed using the Patient Health Questionnaire-8 (PHQ-8).

#### **8.4.6.1 Electronic Self Rated Version, Columbia-Suicide Severity Rating Scale (eC-SSRS)**

The eC-SSRS is a standardized and validated instrument developed for the assessment of the severity and frequency of suicidal ideation and behavior. Subjects respond to standardized clinical questions that are presented in a uniform fashion. The eC-SSRS defines five subtypes of suicidal ideation and behavior in addition to self-injurious behavior with no suicidal intent. The eC-SSRS takes approximately 3 to 10 minutes to complete.

The eC-SSRS questionnaire will be completed by the subject as indicated in the SoA (Section 1.3). It will be completed using an electronic tablet device.

#### **8.4.6.2 Patient Health Questionnaire (PHQ-8)**

The PHQ-8 is a validated and widely used eight-item version of the Patient Health Questionnaire depression scale designed to clinically assess subjects for symptoms and signs of depression. The PHQ-8 takes approximately 3 minutes to complete and will be completed by the subject as indicated in the SoA (Section 1.3). It will be completed using an electronic tablet device.

### **8.5 Adverse Events (AEs) and Serious Adverse Events (SAEs)**

The definitions of an AE or SAE can be found in Section 10.3, Appendix 3.

AEs will be reported by the subject (or, when appropriate, by a caregiver, surrogate, or the subject's legally authorized representative).

The investigator and any qualified designees are responsible for detecting, documenting, and recording events that meet the definition of an AE or SAE and remain responsible for following up AEs that are serious, considered related to the study intervention or study procedures, or that caused the subject to discontinue the study drug.

Adverse events of special interest (AESI) include cytopenias, liver function test changes/enzyme elevations, infections, injection-site reactions, allergic/hypersensitivity reactions, cerebrocardiovascular events, malignancies, depression, Crohn's disease and ulcerative colitis. These events are based on Phase 1 data and findings with other IL-17 modulating drugs. Additional adverse events may be identified as being of special interest during the study and prior to the first unblinding. Formal pre-specified evaluations beyond the discontinuation criteria in Section 7.1 are not planned at this time.

If a subject reports symptoms consistent with a grade 2 serum sickness while between study visits, and causality by the study drug cannot be ruled out, the subject should return to site for an unscheduled visit if symptoms recur after the next dose. There should be a documented assessment and physical examination concurrent with the event

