#### Prior to Week 24:

M1095 subjects in Arms 2 and 3 will receive placebo at Weeks 1, 3, 6, 10 and 14.

M1095 subjects in Arm 4 will receive placebo at Weeks 1, 3, 6, 10, 14 and 16.

M1095 subjects in Arm 5 will receive placebo at Weeks 1, 3 and 14.

Secukinumab subjects in Arm 6 will receive placebo at Weeks 6, 10 and 14.

Subjects randomized to 30mg or 60mg M1095 who do not achieve an IGA score of 0 or 1 at Week 12 will be dose escalated to 120mg q4w starting at Week 12.

Any subjects randomized to M1095 who did not undergo dose escalation at Week 12 and who achieve an IGA score of 0 at Week 24 will have study drug withheld and will receive placebo q4w. Subsequently, if IGA score is 1 or more, these subjects will re-commence M1095 at the dose they received prior to Week 24 on a q4w regimen at the visits scheduled by the protocol until the end of the treatment period. Dose will not be withheld for a second time, irrespective of subsequent IGA scores.

Subjects receiving secukinumab will continue to receive 300mg q4w throughout the study.

The subject blind will be maintained by the use of M1095 and matched placebo. The syringes used for all M1095 and placebo doses will be identical. All subjects will receive two injections of 1mL at each visit. There is also physical protection of the blind. Subjects will be asked to wear an eye-mask for all injections.

Randomization will be stratified by prior biologic use (yes or no) and weight ( $\leq 90$ kg,  $>90$ kg).

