## 6.0 STUDY DRUGS

Study drug is defined as any investigational product, marketed product or placebo, intended to be administered to a study subject according to the study protocol. All study drugs in this study are considered Investigational Medicinal Products (IMP).

Study drugs must NOT be used for any purpose other than as described in this protocol, and this includes other human studies, animal investigations and in vitro testing.

Only subjects enrolled in the study may receive study drugs and only authorised site staff may prepare, supply or administer study drugs.

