### 7.1 Discontinuation of Study Drug

See the SoA (Section 1.3) and Section 8.1.11 for data to be collected at the time of study drug discontinuation, plus follow-up and for evaluations that need to be completed.

Study treatment must be discontinued under the following circumstances (all cases should be discussed with the Medical Monitor):

- Withdrawal of consent
- Emergence of the following:
  - AE considered related to study treatment including:
    - Clinically significant systemic hypersensitivity reaction following administration of study drug that does not respond to symptomatic treatment.
    - Severe (grade 3 or higher Common Terminology Criteria for AEs (CTCAE) Version 5.0) anaphylaxis (symptomatic bronchospasm, with or without urticaria; parenteral intervention indicated; allergy-related edema / angioedema; hypotension).
    - Severe (grade 3 or higher CTCAE Version 5.0) serum sickness (severe arthralgia or arthritis; extensive rash, with steroids or intravenous fluids indicated).
      - Note that if a subject experiences symptoms consistent with a grade 2 serum sickness (moderate arthralgia, fever, rash, or urticaria, with antihistamine treatment indicated), and causality

by the study drug cannot be ruled out, the subject should return to site for an unscheduled visit. There should be a documented assessment and physical examination concurrent with the event. Grade 2 serum sickness does not require discontinuation of study drug, however the Medical Monitor should be informed.

- Any other severe (grade 3 CTCAE Version 5.0) event that does not resolve with supportive care.
- Any life threatening (grade 4 CTCAE Version 5.0) event.
- Any other AE that in the judgment of the investigator, and considering the subject's overall status, prevent the subject from continuing to participate in the study (for example, sepsis or serious infection).
- Laboratory findings as follows regardless of CTCAE Version 5.0 grade:
  - Total WBC count  $<2.00 \times 10^3/\mu\text{L}$ .
  - Total ANC  $<1.00 \times 10^3/\mu\text{L}$ .
  - Platelet count  $<50,000/\mu\text{L}$ .
  - Elevated transaminases (ALT or AST)  $>3 \times$  upper limit of normal (ULN) and associated with total bilirubin  $>2 \times$  ULN (without accompanying alkaline phosphatase elevation  $>2 \times$  ULN suggestive of cholestasis) – i.e. subject meets Hy's Law criteria.

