There is a visit window of  $\pm 1$  day for the Week 4 visit.

Patient reported outcomes (PRO) i.e. PHQ-8, and eC-SSRS should be performed before any other study procedures, assessments or consultations.

IGA, BSA and PASI should be conducted after the PROs and before other tests, procedures and consultations.

Study drug should be administered after completion of all other study procedures.

The following assessments will be performed and information collected:

- PHQ-8
- eC-SSRS
- IGA
- BSA
- PASI
- AEs
- Concomitant Medications
- Skin Evaluation
- Physical Examination
- Vital Signs
- Laboratory Analysis Chemistry and Haematology (Central Laboratory)
- Urine Pregnancy Test (Local) – if positive, study drug must be withheld and a Serum Pregnancy Test (Central Laboratory) performed

- Blood Sample for Immunogenicity (must be pre-dose)
- Blood Sample for Pharmacokinetics (must be pre-dose)
- Study Treatment (allocated via IRT)

#### 8.1.6 Weeks 8, 44, 52

There is a visit window of  $\pm 2$  days for Week 8, and  $\pm 5$  days for Weeks 44 and 52.

Patient reported outcomes (PRO) i.e. PHQ-8, and eC-SSRS should be performed before any other study procedures, assessments or consultations.

IGA, BSA and PASI should be conducted after the PROs and before other tests, procedures and consultations.

Study drug should be administered **after** completion of all other study procedures.

The following assessments will be performed and information collected:

- PHQ-8
- eC-SSRS
- IGA
- BSA
- PASI
- AEs - SAEs and AEs will be followed until resolution, stabilization or the event is otherwise explained or the subject is lost to follow up (see Section 7.3). AEs not considered serious or as an AESI will be considered ongoing if they have not resolved by Week 52.
- Concomitant Medications
- Skin Evaluation
- Vital Signs
- Laboratory Analysis Chemistry and Haematology (Central Laboratory)
- Urine Pregnancy Test (Local) – if positive, study drug must be withheld and a Serum Pregnancy Test (Central Laboratory) performed
- Blood Sample for Immunogenicity (must be pre-dose) – subjects testing positive at Week 52 may be requested to provide another sample 6 to 12 months after study completion
- Blood Sample for Pharmacokinetics (must be pre-dose)
- Study Treatment (allocated via IRT) with the exception of Week 52

- At Week 52, male and female subjects of child bearing potential should be reminded that they must use highly effective contraception for a further 4 weeks

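### Protocol Section 8.5 ties the unscheduled visit for suspected grade 2 serum sickness to a recurrence after the next dose, while Section 7.1 asks for it at the first episode

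*Protocol*

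**What the plan says.** Protocol Section 7.1 (Discontinuation of Study Drug) makes severe serum sickness, grade 3 or higher, a reason to stop study drug. It then deals with the milder case: "Note that if a subject experiences symptoms consistent with a grade 2 serum sickness". Where study drug cannot be excluded as the cause, it directs that "the subject should return to site for an unscheduled visit. There should be a documented assessment and physical examination concurrent with the event". It adds: "Grade 2 serum sickness does not require discontinuation of study drug, however the Medical Monitor should be informed".

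Protocol Section 8.5 (Adverse Events and Serious Adverse Events) returns to the same situation for symptoms reported between study visits, with the same grade and the same causality condition. There the instruction is that "the subject should return to site for an unscheduled visit if symptoms recur after the next dose". The sentence about a documented assessment and examination during the event follows, as in 7.1. The Medical Monitor is not mentioned.

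Two other provisions bear on what the next dose means. Section 6.0 states: "Study drug is defined as any investigational product, marketed product or placebo". Section 4.1 sets the masking injections up to Week 24: "M1095 subjects in Arms 2 and 3 will receive placebo at Weeks 1, 3, 6, 10 and 14". Arm 4 has the same masking weeks, with Week 16 added.

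**The concern.** The two sections give different actions for one event. A subject who telephones with possible grade 2 serum sickness is brought in straight away under 7.1. Under 8.5 the subject is brought in if the symptoms return after another injection. Sites may therefore handle the same possible drug reaction differently, and some may give the next dose without the event-specific examination.

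That examination has a purpose. Section 7.1 stops study drug at grade 3 but lets it continue at grade 2, so someone has to establish the grade. Under 8.5 that judgement may rest on the subject's own report. Section 8.5 also sits awkwardly with itself, because it asks for an examination during the event but defers the visit to a later recurrence, so the first event may never be examined.

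The recurrence condition is also a poor trigger in a blinded trial with masking injections. If the next injection is placebo, the absence of symptoms afterwards says little about whether the active dose caused them, yet under 8.5 no visit follows. At stake is subject safety and consistent conduct, not the efficacy analysis.

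**Working it through.** The plan states no figure on this point. The check is a side-by-side reading, followed by counts from the visit and dosing schedules.

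**The two instructions**

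| | Section 7.1 | Section 8.5 |
|---|---|---|
| Grade | Consistent with grade 2 serum sickness | Same |
| Causality | Study drug not excluded | Same |
| Setting | Not restricted | Reported between visits |
| Unscheduled visit | No further condition | On recurrence after the next dose |
| Examination during the event | Yes | Yes, but attached to the deferred visit |
| Medical Monitor | To be informed | Not mentioned |

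The between-visits qualifier in 8.5 does not separate the cases, since an unscheduled visit arises only between scheduled ones.

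**Text that might reconcile them**

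- Section 8.1.10 permits unscheduled visits on clinical grounds but does not say which trigger applies.
- Section 6.2 wants the Medical Monitor consulted before the next injection, but for acute hypersensitivity after an injection.
- Section 8.4.2 covers a clinically significant rash that does not look like psoriasis; rash is only one of the grade 2 symptoms listed in 7.1.
- Section 8.5.3 and Appendix 3 (Section 10.3) require general follow-up of adverse events.
- The paragraph of 8.5 on events of special interest mentions 7.1, but only for its discontinuation criteria.
- The amendment history in Section 10.8 does not explain the difference.

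None of these settles which instruction governs.

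**Wait to the next dosing visit**

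The Schedule of Activities (Section 1.3) has dosing at Weeks 0, 1, 2, 3, 4, 6, 8, 10, 12, 14, 16, 20, 24, 28, 32, 36, 40 and 44. That is 18 dosing visits, 17 of them after Week 0. The gap between consecutive dosing visits, before visit windows, is:

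- Weeks 0 to 4: 1 week
- Weeks 4 to 16: 2 weeks
- Weeks 16 to 44: 4 weeks

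**Physical examination at the 17 later dosing visits**

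- Schedule of Activities: every dosing visit from Week 4 on, so 17 − 3 = 14. The three without one are Weeks 1, 2 and 3.
- Visit text in Sections 8.1.3 to 8.1.9: Weeks 4, 12, 24 and 36 only, so 4.

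Adverse event review, skin evaluation and vital signs are listed at every one of these visits, and the visit sections say "Study drug should be administered after completion of all other study procedures". These checks therefore come before the next injection, but not necessarily while the reaction is present.

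**How often the injection after an active dose is placebo** (active doses through Week 12, from Sections 4.1 and 6.1)

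| Arm | Active doses, by week | Next injection, by week (P placebo, A active) | Placebo next |
|---|---|---|---|
| 2, 3, 4 | 0, 2, 4, 8, 12 | 1 P, 3 P, 6 P, 10 P, 14 P | 5 of 5 |
| 5 | 0, 2, 4, 6, 8, 10, 12 | 1 P, 3 P, 6 A, 8 A, 10 A, 12 A, 14 P | 3 of 7 |
| 6 | 0, 1, 2, 3, 4, 8, 12 | 1 A, 2 A, 3 A, 4 A, 6 P, 10 P, 14 P | 3 of 7 |

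In Arms 2, 3 and 4, an episode that follows any active dose in this period is always followed by a placebo injection.

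**The case against.** The strongest reply is that the instructions are compatible. Section 8.5 does not restrict the visit to recurrences and does not suspend 7.1, so a site that brings the subject in at the first episode and again on recurrence breaches neither. That is true, but it requires the site to have 7.1 in mind while reading 8.5. Taken alone, 8.5 attaches a condition that 7.1 does not have.

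A second reply is that 8.5 was written for episodes already over when reported, where an examination during the event is impossible and recurrence is the only workable trigger. This reading is plausible. The text does not say it, so it cannot be assumed, but the remedy should allow for it.

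Third, if the Schedule of Activities is followed, as Section 8.0 requires, a physical examination precedes every dose from Week 4 on. This stands, and it narrows re-dosing with no examination at all to Weeks 1 to 3, where the wait is at most one week. It does not supply an examination at the time of the reaction, and the visit text lists far fewer examinations than the schedule.

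Fourth, the terminal half-life of 11 to 12 days (Section 2.3) means M1095 is still present when the placebo injection is given, so non-recurrence is not wholly uninformative. That is fair, and it is why the claim is that it says little. The counts also differ by arm and cover only the period through Week 12.

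Lastly, grade 2 is not a stopping event, both sections allow re-dosing, and the instructions are worded as recommendations. All of this limits the severity but does not remove the conflict.

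**Conclusion.** The concern holds. For a first between-visit episode of suspected grade 2 serum sickness, 7.1 and 8.5 prescribe different actions, and no other text decides between them. It should be fixed.

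Its reach is limited to subjects who report such symptoms between visits. The documents give no rate, so the number cannot be estimated. For those subjects, 8.5 can leave the first episode without its own examination for up to 1, 2 or 4 weeks, and permanently if the symptoms do not return. Sample size, power, error rates and the planned analyses are untouched.

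The conclusion rests on two assumptions: that some site staff will act on 8.5 as it stands without turning to 7.1, and, for the placebo counts, that injections follow the planned schedule through Week 12.

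**What to change.** In Section 8.5, delete the clause that makes the visit depend on recurrence after the next dose, add that the Medical Monitor should be informed, and refer to Section 7.1 as the governing text.

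If 8.5 was intended for episodes that have resolved by the time they are reported, state that. In that case require a documented assessment before the next dose, plus an unscheduled visit if symptoms recur, and leave 7.1 to govern episodes that are still present.

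The cost is a short protocol amendment, a note to sites and a few extra unscheduled visits.

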### **8.5.1 Time Period and Frequency for Collecting AE and SAE Information**

AEs will be collected from the signing of the informed consent form (ICF).

Medical conditions that begin before the start of study drug but after obtaining informed consent will be recorded on the Medical History/Current Medical Conditions section of the eCRF, not the AE section, unless related to study procedures.

All SAEs will be recorded and reported to the sponsor or designee within 24 hours, as indicated in Section 10.3, Appendix 3. The investigator will submit any updated SAE data to the sponsor within 24 hours of it being available.

Investigators are not obligated to actively seek AE or SAE information after the conclusion of a subject's study participation. However, if the investigator learns of any SAE, including a death, at any time after a subject has been discharged from the study, and he/she considers the event to be reasonably related to the study drug or study participation, the investigator must promptly notify the sponsor.

The method of recording, evaluating, and assessing causality of AE and SAE and the procedures for completing and transmitting SAE reports are provided in Section 10.3, Appendix 3.

